
We anticipate this intervention dosage will also affect the study ♀s primary economic outcomes relating to (i) formal workforce participation (ii) housing stability and (iii) financial stability and subsequently reduce economic related HIV risk behaviors such as transactional sex.

Intervention Development Procedures: The intervention development process will entail two design phases. First, we will draft intervention curricula and a trainer ♀s manual based on information obtained during Aim 1 formative research, a review of the existing literature and educational materials from prior successful HIV prevention sessions for TGW and effective content relating to microeconomic interventions in the U.S. Secondly, we will invite the CABs and participating NGOs to advise and provide feedback on the intervention design. During this process, we will also recruit 10 economically and behaviorally vulnerable (as defined above) TGW from each of the 2 study sites (total of 20 TGW) to participate in a 3-day abbreviated session pilot (approximately 4 hours per day) of the five modules. We expect that the 3-day pilot will include an introduction to each module and an accelerated delivery of core module messages, followed by a short discussion on perceived feasibility, acceptability, and fit towards TGW ♀s economic and HIV-related needs. We will pay each TGW test-module participant \$180 for completing the 3-day session (approximately \$15 per hour). After the delivery of each module, a process measure will be administered that assesses the participants' qualitative and quantitative reactions to the material in that module.

Specific Aim 3: Using a randomized experimental study design, evaluate the feasibility and preliminary efficacy of the integrated microeconomic intervention for economically disadvantaged U.S. TGW in reducing economic vulnerability and HIV sexual risk-taking.

Consistent with the program announcement, work during this stage will include testing and further refinement of the intervention manual and implementing a small-scale version of the intervention as a test-of-concept. This small scale RCT is primarily designed to assess feasibility and to estimate intervention parameters (e.g., effect sizes, attrition rates) and to perform preliminary power analyses. The trial will be registered at ClinicalTrials.gov.

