Randomization. Fifty participants in each study site will be randomized to the intervention or wait-list minimal treatment control group. Assuming 80% retention, this will yield a total sample size of 80 (40 in each site). When assigning participants to treatment/control, we will use urn randomization, an adaptive randomization procedure that ensures approximately equal group sizes while approaching complete randomization.⁹⁴ Adherence to the intervention and supervision of interventionists. Sessions will be conducted in private spaces at our community partner locations according to the guidelines in the treatment manual developed in Aim 2. Facilitators will follow checklists developed for each session and will complete a post-session quality assurance form after each session. All study sessions will be digitally recorded. Study investigators will listen to the first recording of each session and provide feedback to interventionists regarding adherence and quality of administration. Thereafter, study investigators will listen to 20% of all recordings (chosen randomly) and provide feedback as needed. To ensure consistency across study site, investigators will listen to audiotapes and provide feedback for both study sites. Monthly group supervision with interventionists will be conducted by the investigators.

Tracking and retention procedures: As it is common for economically marginalized individuals to move frequently and to be financially unable to maintain consistent phone service, comprehensive tracking information will be collected and updated monthly. This information will include home addresses and phone numbers, but also email addresses, social media account information (e.g., Facebook, Instagram) and contact information for individuals who would know how to reach the participants (e.g., friends, family, health care providers, emergency shelter staff). Participants will also be asked to update contact information at the end of each intervention/assessment session. To increase session attendance, we will offset transportation costs.

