Mental health. Participants will complete the 18-item version of the Brief Symptom Inventory (BSI-18).¹⁰⁵ The BSI-18 contains well-validated scales assessing symptoms of depression, anxiety, and somatic distress. Norm information is available. This measure was internally consistent in a TGW sample in our prior work.^{25,88}

Data analysis. Due to the pilot and feasibility objectives and the size limitation of this study, emphasis of the comparative analysis of the intervention impact will focus primarily on estimation of potential mean changes associated with the intervention for planning purposes rather than confirmatory hypothesis testing. GEE models and mixed models would be ideal to use for data analysis; however, since we will be recruiting in two cities and analyzing data across four time points with a relatively small sample size (n=50 to yield final samples of 40), we will use less complex analyses for this study. Baseline characteristics of the two groups will be compared (t-tests for continuous variables, chi-square analyses for dichotomous and other categorical variables). Variables that are significantly different between the two groups at baseline will be controlled for if the sample size allows for us to do so. Two sets of primary analyses will be conducted for this small experimental trial. First, changes over time will be compared between the two groups, using repeated measures ANOVA for continuous variables (e.g., income) and McNemar♦s test for dichotomous variables

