(e.g., % engaged in biomedical prevention strategies of ARV use or PrEP). These mixed repeated measures ANOVAs will be conducted between the groups between baseline and each follow-up time point. We hypothesize that the integrated microeconomic intervention group will have reductions in economic and behavioral vulnerability to HIV relative to the wait-list minimal treatment control group. The second primary analysis will involve simple repeated measures ANOVAs for the integrated microeconomic intervention group only. While potential effects of maturation and history weaken our causal conclusions based on this analysis, because of the relatively small sizes of our two groups we feel it will validate our results of the mixed repeated measures ANOVA between the groups. We will use intent-to-treat analyses, using standard assumptions for those in the intervention group lost to follow-up. We will have .88 power to detect a medium effect size ($f^2 = .25$) for repeated measures ANOVA (assuming $r = .5$ for outcomes over time) and .8 power to detect a medium effect size ($f^2 = .15$ or the equivalent of partial $R = .36$) with three predictors for multiple regression. We will also compute effect sizes for use in future power analyses.

During Aim 3, we will also recruit a small number of individuals (10 total across study sites, 5 in Richmond) who report discrimination from religious organizations on the baseline assessment to participate in 60-90 minute qualitative interviews assessing those experiences. These will be digitally recorded and transcribed for qualitative analysis, similar to Aim 1. All protections used in Aim 1 will also be used here. The qualitative interview guide has been uploaded.

8. * The IRB only reviews research procedures, so differentiate which of the study procedures are:

- a. Being performed exclusively for research purposes (i.e. they would not otherwise be done apart from this study).**
- b. Alterations of routine procedures (e.g. the study is altering the timing, frequency, method, location, amount, etc.).**
- c. Being done for other purposes and whose data/results will be used secondarily in the study (e.g. standard medical or psychological tests, routine education practices, quality improvement initiatives, etc.).**

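### McNemar's test is assigned to comparing change between the randomised arms for yes/no outcomes, but it has no arm term, and the text supplied assigns these outcomes no other between-arm method

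*Combined protocol and SAP*

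**What the plan says.** The relevant text is in Study Procedures, item 7, under Specific Aim 3.

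- **Method.** The first of two primary analyses is described as "changes over time will be compared between the two groups, using repeated measures ANOVA for continuous variables (e.g., income) and McNemar", and the sentence continues with McNemar's test for dichotomous variables. The example given is the percentage "engaged in biomedical prevention strategies of ARV use or PrEP".
- **Hypothesis.** It is comparative: "the integrated microeconomic intervention group will have reductions in economic and behavioral vulnerability to HIV relative to the wait-list minimal treatment control group".
- **Allocation.** Under Randomization, "we will use urn randomization, an adaptive randomization procedure that ensures approximately equal group sizes while approaching complete randomization". No matching or pairing of participants is described.
- **Purpose.** The trial is "primarily designed to assess feasibility and to estimate intervention parameters (e.g., effect sizes, attrition rates) and to perform preliminary power analyses". The Data analysis text places estimation first, "for planning purposes rather than confirmatory hypothesis testing", and ends its power statement with "We will also compute effect sizes for use in future power analyses".
- **Outcomes.** Under Assessment procedures and measures, the primary indicators include several that are naturally yes/no: verified HIV testing, linkage to care, PrEP enrolment (HIV-negative), a current ARV prescription (HIV-positive) and engagement in transactional sex.

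**The concern.** The stated task is to compare change between two independent randomised arms. The named method handles paired yes/no data from a single sample. An analyst following the sentence literally would have to choose a way to run the test, and none of the choices yields a between-arm result.

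The pilot status does not make this harmless. Because the plan puts estimation ahead of testing, the between-arm estimate is the main product of the trial and the input to the next power calculation. McNemar's test gives neither a between-arm effect size nor an interval. A reader could work one out from arm-level proportions, but the plan does not say these will be reported.

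**Working it through.** **1. Is there a stated figure to reproduce?** No. The plan gives no rate, effect size or power for any dichotomous outcome. Its power figures are for repeated measures ANOVA and multiple regression.

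**2. Ways to run McNemar's test here.** The exact test uses only discordant pairs: b gains and c losses, with p = 2 × P(X ≤ min(b, c)), X ~ Binomial(b + c, 0.5). Arm appears nowhere.

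| Way of running it | What it tests |
|---|---|
| Within each arm | That arm's own change from baseline |
| Both arms pooled | Overall change, ignoring arm |
| Across arms | Needs matched pairs, which do not exist |

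Worked example: in both arms 10 of 40 gain and 2 of 40 lose.
- Each arm: 2 × (1 + 12 + 66)/4096 = 0.039.
- Pooled (20 gains, 4 losses): p = 0.0015.
- Between-arm difference in change: (10 − 2)/40 − (10 − 2)/40 = 0.

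All three McNemar tests are significant although the arms are identical.

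**3. Does another method fill the gap?**
- Chi-square is named for baseline characteristics only.
- GEE and mixed models are called ideal and then set aside.
- The between-group sentence that follows covers the mixed ANOVAs only.
- The second primary analysis is ANOVA within the intervention arm.
- Multiple regression appears only in the power statement, "with three predictors for multiple regression", with no outcome or predictors named.

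**4. Size, if the test were run arm by arm.** This is an assumption, as are all rates. Simulation: 40 per arm (80 retained in total, from Randomization), baseline 20%, no arm effect, within-person correlation 0.2 / 0.4 / 0.6, exact two-sided McNemar at 0.05, 40,000 trials per scenario.

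| Both arms move to | Intervention arm significant | Intervention significant, control not |
|---|---|---|
| 20% | 2 / 2 / 1% | 2 / 2 / 1% |
| 25% | 5 / 5 / 5% | 5 / 5 / 4% |
| 30% | 13 / 16 / 19% | 11 / 13 / 16% |
| 40% | 48 / 60 / 82% | 25 / 24 / 15% |

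The Newcombe 95% interval for the follow-up risk difference excludes zero in about 5% throughout.

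The error also runs the other way. If intervention stays at 20% and control falls to 10%, the intervention-arm test is significant in 1% to 2% of trials, against about 24% for the between-arm interval.

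Shared change is plausible. Under Compensation, controls get an abbreviated intervention, and the Aim 3 email script places it at six months. The documents give no rates, so its size is unknown.

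**5. Precision of the replacement.** With equal proportions p and Wilson limits l and u, the Newcombe half-width is √[(p − l)² + (u − p)²].
- n = 40, p = 0.2: l = 0.105, u = 0.348, giving 17.6 points. At p = 0.5: 20.9 points.
- n = 50 (all randomised): 15.7 and 18.9 points.
- By HIV status, if the US prevalence estimates in the Background (21.7% and 27.7%) applied here: 40 × 0.217 = 8.7 and 40 × 0.277 = 11.1. That is about 9 to 11 HIV-positive per arm (half-width 33 to 39 points) and 29 to 31 HIV-negative (20 to 24 points).

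**6. Does using baseline help?** Assume 30% to 50% against 30% to 30%, 40 per arm. The unadjusted interval excludes zero in about 46% of trials. A baseline-adjusted linear model does so in 45 / 50 / 61% at correlation 0.2 / 0.4 / 0.6. Adjustment costs almost nothing at low correlation and gains at higher correlation.

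**The case against.** Five points can be made for the plan.

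- **A suitable tool may already be there.** The plan powers a three-predictor regression and says baseline-imbalanced variables will be controlled for where the sample allows. A model with arm, baseline status and site has three predictors. This stands as far as it goes: the right claim is that no between-arm method is *specified* for these outcomes. A reader might infer that the investigators have none at all. The documents do not support that, since the form says it pastes only part of the grant application, which is not available here.
- **It is a pilot, and effect sizes are promised.** The promise is not limited to continuous outcomes. But no measure is named for binary ones, and the named test does not produce one.
- **Nothing is lost.** Paired yes/no data will be collected and would support any later between-arm estimate. This is true and keeps the repair small.
- **The error rates are conditional.** A reader might infer that the trial will produce many false positives. The documents do not say the test will be run arm by arm and give no rates, and the large percentages need shared changes of 10 to 20 points.
- **A follow-up-only difference would not answer the plan's question.** The plan asks about change from baseline, and discarding baseline can cost precision (step 6). This stands, so the main replacement should use baseline status.

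**Conclusion.** The concern holds, and the sentence should be corrected before analysis. McNemar's test cannot compare the two arms, and in the text supplied nothing else is assigned to do so for dichotomous follow-up outcomes. That conclusion follows from the design and the definition of the test and rests on no assumed rate.

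The size is illustrative: about 13% to 19% intervention-arm significance under a shared rise from 20% to 30%, and little or no inflation at 5 points or less. It assumes arm-by-arm use, 40 completers per arm, a 20% baseline and correlations of 0.2 to 0.6.

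A reader might extend this to the whole efficacy analysis. That would be wrong: the mixed repeated measures ANOVA does contain a between-arm contrast, and continuous outcomes are not touched by this point.

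**What to change.** Replace McNemar's test in the between-arm analysis as follows.

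1. For each dichotomous outcome at each follow-up, report the between-arm risk difference with a 95% confidence interval from a linear model with robust standard errors on arm, baseline status and site.
2. Alongside it, report the unadjusted risk difference with a Newcombe interval. Make this the main result where the adjusted model cannot be fitted, for example in a small HIV-positive subgroup.
3. Report arm-level proportions at every time point.
4. State whether ARV and PrEP use form one composite over everyone or two outcomes by HIV status.
5. McNemar's test may stay as a within-arm description. Leave the mixed ANOVA as it is.

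The cost is a change of wording, with no new data or participants. The downside is visibly wide intervals: about 18 to 21 points either side, unadjusted, at 40 completers per arm, or about 16 to 19 if all 50 per arm are included under intention to treat. ARV use in HIV-positive participants alone could reach about 39 points. These figures treat participants as independent and make no allowance for delivery in groups.

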This will include 30 TGW (15 in each site) for qualitative interviews which we believe will be enough to achieve saturation, 20 TGW (10 in each site) for pilot testing of intervention (we believe this will match the size of the intervention group and thus is appropriate for intervention piloting), and 100 TGW (50 in each site) for the randomized controlled trial. The total number above also reflects the numbers we anticipate screening for study inclusion. This will include some individuals who are not eligible and some individuals who are eligible but choose not to participate in study activities other than completing the screening survey. For the RCT the size is justified by power analysis. We will use intent-to-treat analyses, using standard assumptions for those in the intervention group lost to follow-up. We will have .88 power to detect a medium effect size ($f^2=.25$) for repeated measures ANOVA (assuming $r = .5$ for outcomes over time) and .8 power to detect a medium effect size ($f^2 = .15$ or the equivalent of partial $R = .36$) with three predictors for multiple regression.

4. * List the study inclusion criteria:

For screening, inclusion criteria will include that the participant is a transgender woman and is 18-45 years of age.

For TGW, full study participation, inclusion criteria will require both (i) Economic vulnerability (unemployment or underemployment [less than 20 hours/week], low income [less than the Medicaid poverty threshold], housing insecurity in the past year, or food insecurity in the past year), and (ii) Behavioral vulnerability to HIV transmission: unprotected sex in prior 6 months, transactional sex, multiple sexual partners, 1-time sexual partner, sex with a partner of unknown HIV status, sex under the influence of drugs or alcohol. Participants will be recruited if they are age 18 or older. Based on our prior work, we expect participants meeting these guidelines to be relatively young (mean age = 32, SD =10) and predominantly African American. Based on data from our pilot work, we expect around 45% of individuals screened to meet eligibility requirements.

These are the inclusion criteria for TGW for Aims 1, 2, and 3.

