Assessment procedures and measures: Assessments will be conducted at baseline, 3 months post-intervention, 6 months post-intervention, and 9 months post-intervention. Graduated incentives will be used: \$20 for the baseline assessment, \$25 for the 3-month assessment, \$30 for the 6-month assessment, and \$35 for the 9-month assessment. In addition, individuals who complete all 4 assessments will receive a \$50 bonus. Incentives will be prorated contingent on completion of both the objective and subjective indicator outcomes.

Primary outcomes will be economic and behavioral vulnerability to HIV, both of which will be assessed via objective and subjective indicators. Objective indicators for economic vulnerability will include verification of employment, income, housing stability, and savings. Participants will be asked to show a copy or image of a recent pay stub, lease, and bank statement. We will also conduct home visits to verify stable living arrangements and will have information from employers (e.g., hours worked) for participants who are employed through the employment assistance program. Objective indicators for behavioral vulnerability will include verification of HIV testing, verification of linkage to care, verification of enrollment in PrEP (for HIV- participants) and verification of a current prescription for ARVs (for HIV+ participants). Participants will be asked to show a copy or image of a recent physician visit statement or receipt, HIV test result, and/or medication label. Pill counts will be used to assess adherence to biomedical prevention approaches.⁹⁶⁻⁹⁸ Participants will be prompted in advance to bring objective indicators to the assessments but it will also be possible for them to provide information afterwards (e.g., by taking a photo of a bank statement or prescription label and texting it to the project or during a home visit). Subjective indicators for economic vulnerability will include self-reported employment status, hours worked, income, housing status, and savings. Subjective indicators for behavioral vulnerability will include self-reported engagement in transactional sex, number of CSW transactions and partners, unprotected anal/vaginal sex, number and type of sexual partners, and self-reported substance use in conjunction with sexual activity.

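### An intervention-only before-after ANOVA is made a second primary analysis and said to validate the randomised comparison, which it cannot do

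*Combined protocol and SAP*

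**What the plan says.** The analysis plan is in Study Procedures, item 7, Specific Aim 3, under Data analysis. It states: "Two sets of primary analyses will be conducted for this small experimental trial". The first set compares change over time between the randomised groups. Then: "The second primary analysis will involve simple repeated measures ANOVAs for the integrated microeconomic intervention group only". The plan gives a caveat, "While potential effects of maturation and history weaken our causal conclusions based on this analysis", but goes on to say, citing the small groups, that "we feel it will validate our results of the mixed repeated measures ANOVA between the groups". No order or hierarchy between the two sets is given.

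Study Population, item 4, sets two entry requirements. The first is "Economic vulnerability (unemployment or underemployment [less than 20 hours/week], low income [less than the Medicaid poverty threshold], housing insecurity in the past year", with food insecurity in the past year as a further alternative. The second is behavioural vulnerability: unprotected sex in the prior 6 months, transactional sex, multiple, one-time or unknown-status partners, or sex under the influence.

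The primary outcomes, in the assessment paragraphs of Study Procedures, item 7, are economic and behavioural vulnerability. On the economic side: "Subjective indicators for economic vulnerability will include self-reported employment status, hours worked, income, housing status, and savings". The behavioural self-reports cover transactional sex, unprotected sex, partners and substance use with sex. There are also objective indicators: pay, lease and bank documents, HIV testing, linkage to care, PrEP enrolment, ARV prescription and pill counts.

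**The concern.** A primary analysis with no control group attributes to the intervention every change that would have happened anyway. The plan concedes this in part and still gives the analysis primary status and a confirming role. Small groups make the control arm noisier, but leaving that arm out does not check the result obtained with it.

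This design adds a specific source of untreated change. Women are enrolled partly because they meet criteria on items later scored as outcomes. People chosen at a poor value tend, on average, to move back towards their usual level. Randomisation cancels that drift because both arms share it; a one-arm ANOVA counts it as effect.

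Two things are at stake. A null randomised comparison could be reported beside a significant primary within-arm improvement as preliminary efficacy. And the plan will compute effect sizes for future power analyses without saying which contrast supplies them; a within-arm change that contains drift would make the next trial too small.

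**Working it through.** **The plan's own figure.** The plan states .88 power for repeated measures ANOVA at a medium effect of .25 with r = .5. Taking .25 as f, 4 visits, N = 100 and alpha .05 (not stated; assumed), the between-groups test has noncentrality f²·N·m/(1+(m−1)r) = .0625 × 100 × 4/2.5 = 10 and power .879, which reproduces .88. At the 80 expected to be retained it is .798. The plan gives no operating figure for the one-arm test.

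**Why it cannot validate.** Write the arms' mean changes as ΔI and ΔC. The randomised contrast is D = ΔI − ΔC; the one-arm analysis tests ΔI alone. With treatment effect τ and shared untreated drift δ, the expectation of ΔI is τ + δ and that of D is τ. The two are also not independent. With equal arms and equal variance V, cov(ΔI, D) = V and var(D) = 2V, so their correlation is V/√(V × 2V) = .71 whatever τ is. Some agreement is therefore built in and confirms nothing.

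**Size of the drift from selection, with τ = 0.** Inputs: 45% of screened women eligible (Study Population, item 4); r = .5 over time (power statement); 50 per arm and 80% retention, so 40 (Aim 3 and Randomization). SD means the SD in the unselected screened population, with normal outcomes assumed.

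1. *Selected mean.* For the worst 45% on one score, z = 0.126 and the mean is φ(z)/.45 = 0.880.
2. *Baseline is the selection score.* Drift = (1 − .5) × 0.880 = 0.44 SD. The variance of the selected score is 1 − 0.880(0.880 − 0.126) = 0.337. The variance of change is .25 × 0.337 + .75 = 0.834, so its SD is 0.913. Noncentrality is 0.44/0.913 × √40 = 3.05, and a paired test of baseline against one follow-up rejects 84% of the time.
3. *r = .5 among enrolled women.* A screened-population r of .5 becomes .32 after this selection. To have .5 among those enrolled, r² = .25/(.75 × 0.337 + .25) = 0.497, so r = .705. Drift = .295 × 0.880 = 0.26 SD, the SD of change is 0.729, and rejection is about 59%.
4. *Baseline is a separate measurement.* If it correlates q with screening and follow-up correlates .5, drift = (q − .5) × 0.880.

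Simulation with no effect, 40 per arm and 3,000 replicates compared the one-arm ANOVA over four visits with the randomised group-by-time test. In the either/or case (an assumed structure) the outcome is one of four alternative economic criteria. The other three correlate .3 with it, and 67% pass the domain (.67 × .67 ≈ .45 for both domains).

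| Screen-baseline correlation q | Single score: drift, one-arm rejection | Either/or: drift, one-arm rejection |
|---|---|---|
| .5 | 0 SD, 5% | 0 SD, 5% |
| .7 | 0.18 SD, 17% | 0.08 SD, 7% |
| .9 | 0.35 SD, 65% | 0.15 SD, 13.5% |
| 1.0 | 0.44 SD, 87% | 0.19 SD, 20% |

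The randomised test rejected 4% to 5% of the time in every cell.

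**The case against.** A reader might infer that every enrolled woman must have a bad current value on the outcomes, so that a false positive in more than 80% of null trials is to be expected. The documents do not support that:

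- The economic criteria are alternatives. Food insecurity alone suffices and is not a listed outcome. Housing and food look back a year, and unprotected sex six months.
- Savings, HIV testing, linkage to care, PrEP, ARV prescription and pill counts are not entry criteria, so the regression argument does not reach them.
- Screening and baseline use different instruments (Documents list). Drift that occurs between them does not enter change from baseline. The Aim 3 consent page allows only days between screening and the first session, which makes a high correlation plausible but does not establish it.
- The 45% is a joint pass rate over many criteria, not a cut on one outcome.

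All of this stands, and it limits the size of the drift.

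It is also fair that the plan puts its emphasis on estimation rather than confirmatory testing, admits weakened causal conclusions, and does not say that within-arm effects will feed the power calculations. The recruitment script offers control participants an abbreviated workshop at six months, so a nine-month contrast may be diluted. These are reasons to show within-arm change descriptively. They do not justify primary status or the validation claim, which fail even if the drift is zero. An estimation focus makes a biased estimate more consequential.

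**Conclusion.** The point holds. The intervention-only ANOVA has the wrong role as written: it cannot validate the randomised result, and that conclusion needs no assumption about drift. Regression to the mean is a real but unquantified additional threat for the outcomes that overlap with entry: employment, hours, income, housing, transactional and unprotected sex, partners, and substance use with sex.

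Under the inputs above, its size runs from zero, when baseline is no more correlated with screening than follow-up is, to 0.44 SD, when baseline is the selection score itself. The either/or case comes nearest to the actual criteria, at 0.08 to 0.19 SD and 7% to 20% rejection for q from .7 to 1.0, but its structure is assumed. The 84% figure is the upper end of these inputs and not a forecast. Skewed counts and binary items would change the numbers, not the direction.

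**What to change.** In the Aim 3 data analysis text:

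- Keep the between-arm comparison as the only primary efficacy analysis.
- Relabel the intervention-only ANOVA as secondary and descriptive, and delete the statement that it validates the between-arm result.
- Report within-arm change for both arms side by side.
- Name regression to the mean beside maturation and history, and list the outcomes that overlap with the entry criteria.
- State that efficacy effect sizes for future power calculations come from the between-arm difference.

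The cost is protocol wording. Sample size, data collection and procedures do not change. The downside is that a test likely to look favourable loses its primary status.

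### The .88 power for repeated measures ANOVA does not follow from the printed f² = .25; read as f = .25 it best fits a four-visit main effect at N = 100, not the planned baseline-to-follow-up comparison

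*Combined protocol and SAP*

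**What the plan says.** Study Population, item 3, rests the trial size on this calculation: "For the RCT the size is justified by power analysis". The figure for the main method follows there ("We will have .88 power to detect a medium effect size ($f^2=.25$) for repeated measures ANOVA") and is repeated in Study Procedures, item 7, Specific Aim 3, Data analysis ("We will have .88 power to detect a medium effect size ($f^2 = .25$) for repeated measures ANOVA"). Both places assume r = .5 over time. The same sentence then gives .8 power for a three-predictor regression: "8 power to detect a medium effect size ($f^2 = .15$ or the equivalent of partial $R = .36" (the leading 8 is the .8).

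On numbers, Aim 3 has 50 per arm, 100 in all. The Randomization paragraph adds: "Assuming 80% retention, this will yield a total sample size of 80 (40 in each site". Data analysis speaks of a "relatively small sample size (n=50 to yield final samples of 40".

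On the analysis, the first primary set compares change over time between the arms: "These mixed repeated measures ANOVAs will be conducted between the groups between baseline and each follow-up time point". The second is within one arm: "The second primary analysis will involve simple repeated measures ANOVAs for the integrated microeconomic intervention group only".

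Neither power statement gives alpha, the tested term, the number of visits or the N used.

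**The concern.** The sentence prints one symbol, f², with the label 'medium' attached to two values: .25 for the ANOVA and .15 for the regression. The regression value agrees with its own partial R. The ANOVA value looks like f = .25 written as f² = .25, a fourfold difference in f² (.25 against .0625).

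If so, the printed power is wrong for the printed effect. Correcting the symbol also leaves open which test and which sample the .88 describes. The plan says the RCT size is justified by power analysis, so a reader should be able to reproduce the figure and tie it to a comparison that will be made.

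**Working it through.** **Inputs.** Power .88, f² = .25 and r = .5 (Data analysis; Study Population, item 3). N = 100 randomized (Aim 3) or 80 retained (Randomization). Visits m = 4 in all, or m = 2 for baseline against one follow-up (Data analysis). Two-sided alpha .05 is my assumption; .01 is also shown.

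**Formulas** (noncentral F, two equal arms):
- Between-group main effect: λ = N·m·f² / (1 + (m − 1)r), df 1 and N − 2.
- Group-by-time: λ = N·m·f² / (1 − r), df m − 1 and (N − 2)(m − 1).

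**Step 1. The plan's figure as printed, f² = .25.** The least favourable of these terms is the main effect over two visits.
- N = 80: λ = 80·2·.25/1.5 = 26.7; power .9992 (.993 at alpha .01).
- N = 100: λ = 100·2·.25/1.5 = 33.3; power .9999 (.999 at alpha .01).
- Group-by-time exceeds .9999 at both N.

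The .88 is not reproduced. If f² is taken to absorb r already, two visits still give .992 to .993 at N = 80 and .998 to .999 at N = 100.

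**Step 2. The scale used in the same sentence.** Partial R = √(f²/(1 + f²)). For f² = .15, √(.15/1.15) = .361, which agrees with the printed .36. For f² = .25, √(.25/1.25) = .447. The regression clause uses f² correctly; the ANOVA clause cannot be on the same scale with the same label.

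**Step 3. Read as f = .25 (f² = .0625), alpha .05.**

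| Term | Visits | N = 80 | N = 100 |
|---|---|---|---|
| Between-group main effect | 4 | λ = 8, .798 | λ = 10, **.879** |
| Between-group main effect | 2 | λ = 6.7, .722 | λ = 8.3, .816 |
| Group-by-time | 2 | λ = 20, .993 | λ = 25, .999 |

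The match to .88 is the four-visit main effect with all 100 randomized. That term averages baseline in with the follow-ups.

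**Step 4. The planned comparison.** With two arms and two visits, a between-arm difference in change of d outcome SDs gives f = d/4. So f = .25 means d = 1.0 SD, which is the .993 (N = 80) in the table.

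The same contrast is a two-sample t-test on change scores. The SD of change is √(2(1 − r)) outcome SDs, which is 1 at r = .5. The normal approximation for 80% power is d ≈ 2.80·√(2/n): 0.626 for n = 40 per arm and 0.560 for n = 50. The exact noncentral t values are **0.634** and **0.566**.

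**Step 5. The companion regression figure.** With f² = .15, three predictors and λ = N·f² on 3 and N − 4 df, power is .802 at N = 77, .819 at N = 80 and .905 at N = 100. The stated .8 therefore fits the retained sample, while the best match for .88 needs the randomized sample.

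**The case against.** The best defence is that this is one mistyped symbol in a feasibility pilot. Data analysis puts the emphasis on estimation for planning rather than on confirmatory testing, and Specific Aim 3 describes the RCT as primarily for feasibility and parameter estimates. The plan also calls for intent-to-treat analysis, so N = 100 may be deliberate, and .88 would then be right for the four-visit main effect. Much of this stands, and it limits the consequence. It does not make the printed sentence correct, and it does not connect .88 to the two-visit comparison that is planned.

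Four stronger readings are tempting but not supported.
- **The trial is underpowered or its design invalid.** The stated purpose is feasibility and estimation, and the documents define no target difference in SD units against which power could be called inadequate.
- **No effect scale is given, or the origin of .88 is wholly obscure.** A scale is printed; the problem is that it conflicts with .88. At f = .25 and alpha .05, the two-visit interaction with N = 40, or one arm with n = 40, gives .869, which rounds to .87. The four-visit main effect at N = 100 is the better fit. It is not certain, because alpha is unstated: at alpha .10 the same term gives .877 with N = 80.
- **The regression figure belongs to the adjustment for baseline imbalance.** Data analysis describes no multiple regression, so that link cannot be made.
- **The missing inputs were never specified.** They may be in the grant application listed among the uploads, which is not available here. The two power statements do not give them.

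**Conclusion.** The concern holds as a reporting error that should be fixed. At the printed f² = .25 and r = .5, power is .9992 or more at N = 80 or 100 (alpha .05) and .993 or more at alpha .01, not .88. The printed scale also conflicts with the regression clause beside it.

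Read as f = .25, which is probable but is my inference, .88 corresponds to the four-visit group main effect at N = 100 (.879), falling to .798 with the 80 expected to be retained. It is not the power of the planned baseline-to-follow-up group-by-time test, where f = .25 would mean a 1.0 SD difference in change. The two power figures in the sentence appear to use different N.

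The detectable differences of 0.63 and 0.57 SD assume two-sided .05, the plan's r = .5, equal SDs at both visits and equal retention by arm; the plan gives 40 retained per site, not per arm.

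**What to change.** In Study Population, item 3, and in Data analysis:

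1. Write f = .25 (f² = .0625) for the ANOVA in place of f² = .25, once the investigators confirm that this was the input.
2. State alpha, the tested term, the number of visits and the analysed N. Use one N for both figures: about .80 (ANOVA main effect) and .82 (regression) at N = 80, or .88 and .90 at N = 100.
3. Either label .88 as the four-visit between-group main effect with 100 analysed, adding that it is about .80 with 80, or replace it with the planned contrast. Possible wording: *For the group-by-time comparison of baseline with one follow-up (two visits, two-sided alpha .05, r = .5, equal SDs and equal retention by arm), 80% power requires a between-arm difference in change of 0.63 SD with 40 analysed per arm, or 0.57 SD with 50.*

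The cost is a few sentences in two places. The stated power may look less favourable, but enrolment, visits and analyses stay as they are, and the feasibility and estimation purpose is unaffected.
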